### 3.2.2. Open-label Booster Phase

Participants will enter the booster phase on the day that the participants completed the booster visit until consenting to Amendment 7 (or with the stop of the eCOA at each study site, whichever date comes first). There are 3 main cohorts based on vaccination schedules received in the booster phase:

- Homologous boost cohort consists of following 2 groups:
  - participants who were initially randomized to the Ad26.COV2.S group and received 1 dose of Ad26.COV2.S at day 1 within the trial and a booster dose preferably within 6 to 12 months after the initial vaccination, with a minimum of 3 months after the initial vaccination with Ad26.COV2.S
  - participants who were initially randomized to the placebo group and who received 1 dose of Ad26.COV2.S after unblinding and a booster dose preferably within 6 to 12 months after the initial vaccination, with a minimum of 3 months after the last vaccination with Ad26.COV2.S
- Heterologous boost cohort: participants who were initially randomized to the placebo group and who received an mRNA vaccination outside of the trial and an Ad26.COV2 booster dose preferably within 6 to 12 months after the initial vaccination, with a minimum of 3 months after the last outside vaccination
- Non-boost cohort: participants who received 1 Ad26.COV2.S vaccination, either at Day 1 or as a cross-over vaccination. These participants remain in this cohort until they receive the booster vaccination. Participants who opt not to receive a booster dose will continue in this cohort.

Data from participants who received a different sequence of vaccinations (eg, Ad26.COV2 prime vaccination and an outside booster) will be presented separately.

The main objective of the booster phase of the study is to evaluate the COVID-19 outcomes, safety, and immunogenicity of the different schedules that were assessed: homologous Ad26.COV2 booster schedule, 1-dose schedule, heterologous booster schedule. All analyses are descriptive, efficacy evaluations may be done if feasible, ie, if pre-specified criteria are met, and will be described in the SAP.

The primary, secondary, and exploratory objectives and endpoints for the booster phase of the study are:

Objectives	Endpoints
Primary (Booster Phase)	
To assess the safety and reactogenicity of Ad26.COV2.S at the $5 \times 10^{10}$ vp dose level administered as homologous or heterologous booster vaccination in adults.	
 
• Solicited local and systemic AEs for 7 days after booster vaccination.
 
• Unsolicited AEs for 28 days after booster vaccination.
 
• SAEs and AESIs from booster vaccination until end of the study.
 

Objectives	Endpoints
To evaluate the primary endpoints previously utilized for the double-blind portion of the study in this unblinded booster portion of the trial during the time participants have and have not been boosted.	
 
Incidence of primary endpoints utilized in the double-blind portion of the study, including moderate to severe/critical COVID-19 cases starting at 28 days by serostatus*, in the unblinded booster portion of the study (see definitions of terms in Section 10.1) during the times when they have and have not been boosted.
 

To evaluate the primary endpoints previously utilized for the double-blind portion of the study in participants infected with selected variants and the reference strain in this unblinded booster portion of the trial during the time participants have and have not been boosted.	
 
Incidence of primary endpoints (Day 28 after vaccination) in the main study as applicable as described in the first objective but for variants of concern and the reference variants.
 

Secondary (Booster Phase)	
To evaluate the secondary endpoints previously utilized for the double-blind portion of the study in this unblinded booster portion of the trial during the time participants have and have not been boosted.	
 
Incidence of secondary endpoints (Day 28 after vaccination) from the double-blind portion of the study by serostatus* such as symptomatic severe/critical disease, hospitalization, and death.
 

To evaluate the primary and secondary endpoints utilized in the double-blind portion of the study in this unblinded booster portion of the trial in participants primed or boosted with Ad26.COV2.S, mRNA, inactivated, protein, and other adenovector-based vaccines during the time participants have and have not been boosted.	
 
Description of the primary and secondary endpoints (Day 28 after vaccination), such as symptomatic, severe/critical disease, hospitalization, and death, in the double-blind portion of the study as applicable as described in the first primary objective and first secondary objective including variants of concern and reference variants.
 

To estimate a correlate of immunity (correlate of risk) in relation to the primary endpoint of the main study and serious disease, hospitalization, and death based on immune responses at Day 28 after booster vaccination in boosted compared to non-boosted participants.	
 
Serological response to vaccination and antibody titers (VNA) against the original strain, 28 days after Ad26.COV2.S (<math>5 \times 10^{10}</math> vp dose level) single-dose booster vaccination.
 

To estimate potential correlate of risk/efficacy in relation to the primary endpoint of the main study and serious disease, hospitalization, and death based on immune responses in breakthrough cases compared to non-infected participants.	
 
Levels of immune responses (antibody titers) and RNA sequencing analysis as available.
 

To compare the immune responses in the Heterologous and Homologous Booster Subsets 28 Days following booster dose administration.	
 
Qualitative comparison of responses in terms of binding, neutralizing antibody against Wuhan reference strain and variants of interest utilizing wtVNA and/or psVNA, depending on feasibility.
 

Objectives	Endpoints
	
 
Analysis of antibodies binding to the SARS-CoV-2S protein by ELISA.
 

To evaluate SARS-CoV-2 infection (severe/critical, moderate to severe/critical, moderate, symptomatic, and asymptomatic infections, that are serologically and/or molecularly confirmed**) for the different cohorts	
 
Incidence of SARS-CoV-2 infections (serologically and/or molecularly confirmed**).
 

To describe the severity of SARS.COV2.S infections	
 
The severity of COVID-19 cases may be evaluated by the severity and number of symptoms (severity) of COVID-19 cases, ratio of severe/critical COVID-19 cases and ratio of long COVID-19 cases (duration of more than 28 days)
 

To obtain samples to evaluate potential thromboembolic events following booster immunization by obtaining platelet counts and sufficient extra sera for specialized studies at the day of booster immunization and 28 days later.	
 
Platelet count on the day of booster vaccination and 28 days after booster vaccination. Additional analysis on kept sera samples in case of potential thromboembolic events.
 

Exploratory (Booster Phase)	
To measure the primary and secondary endpoints previously utilized in the double-blind portion of the study for all participants who have received any SARS-CoV-2 booster vaccine outside the study within the past month, are N-serology seronegative*, and remained in the unblinded booster portion of the study during the time when they have and have not been boosted. To utilize this data to explore estimates of efficacy comparing boosted to unboosted periods and by utilization of real-world data control groups constructed of vaccinees that are not boosted, if feasible.	
 
Estimation of the primary and secondary endpoints in the main study, as applicable, and described above.
 

To measure moderate to severe/critical and severe/critical endpoints as defined for the double-blind portion of the study in participants who were N ELISA sero-negative and those who were N ELISA sero-positive at the time they received their booster. To utilize this data to compare rates of these endpoints in participants who are seropositive vs those that are seronegative* at the time they received their booster.	
 
Describe rates of infection for moderate to severe/critical as defined and determined by the protocol in boosted participants who are N-serology seropositive versus those that are N-serology seronegative* at the time of booster vaccination.
 

An attempt to estimate the duration of protection following booster vaccination with Ad26.COVID2.S for the primary and secondary endpoints will be made as outlined in the SAP.	
 
Estimation of the primary and selected secondary endpoints in the main study as applicable.
 

Objectives	Endpoints
To estimate if there is a relationship between efficacy and the time period between priming COVID-19 vaccination regimen and Ad26.COV2.S booster vaccination.	
 
Estimation of the primary and selected secondary endpoints in the main study as applicable.
 

To compare the immune responses in the Heterologous and Homologous Booster Subsets compared to the immune responses observed in the VAC31518COV2008 boosting study and in this study after primary vaccination.	
 
Qualitative comparison of responses in terms of binding (S and/or RBD), neutralizing antibody against Wuhan reference and variants of interest utilizing wVNA and/or psVNA, depending on feasibility.
 

To analyze for signs of inflammation, coagulation pathway disorders, and markers of potential correlates of protection in a subset of participants from the Heterologous and Homologous Booster Subsets at baseline (prior to booster vaccination), 1 day, and 28 days after booster vaccination, depending on feasibility.	
 
mRNA sequencing immediately after immunization up to 28 days after vaccination analyzed in participants who received booster vaccination compared to responses after primary immunization following immunization of cross-over participants from the placebo group at unblinding in VAC31518COV3001 and VAC31518COV2008 for differences in gene expression.
 
Cytokine profiling: Analysis of cytokines, chemokines, and other proteins of the innate or adaptive immune response in the serum or plasma.
 

To further assess the humoral immune response to Ad26.COV2.S, in participants from the Homologous and Heterologous Booster Subsets	
Exploratory analyses may include, but are not limited to, the following assays:
 
 
SARS-CoV-2 neutralization as assessed by alternative SARS-CoV-2 neutralization assays (VNA).
 
Adenovirus neutralization.
 
Functional and molecular antibody characterization including Fc-mediated viral clearance, avidity, Fc characteristics, Ig subclass and IgG isotype.
 
Epitope-specificity characterization of antibodies.
 
Passive transfer: Analysis of immune mediators correlating with protection against experimental SARS-CoV-2 challenge in a suitable animal model.
 

\* Seronegative is defined as N-serology seronegative at the time of boosting or at the Year 1 visit if not boosted

\*\* Molecularly confirmed COVID-19 is defined as a positive SARS-CoV-2 viral RNA result by a central laboratory using a RT-PCR based or other molecular diagnostic test.

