### 2.1 Open-label Cross-over Phase

Participant will enter the open-label crossover phase on the day that the participant received the cross-over vaccination or is unblinded until the day that the participant completed the booster visit. There are 2 main cohorts in the open-label phase:

- Early vaccinated cohort: participants who were initially randomized to the Ad26.COVID2.S group and received 1 dose of Ad26.COVID2.S at Day 1 in the trial
- Late vaccinated cohort: participants who were initially randomized to the placebo group and who received 1 dose of Ad26.COVID2.S after unblinding

The main objective of the open-label phase of the study is to evaluate the COVID-19 outcomes after an early vaccination and after a late vaccination. Efficacy evaluations may be performed if feasible, ie, if pre-specified criteria are met, as specified in the SAP.

The secondary and exploratory objectives and endpoints for the open-label phase of the study are:

Objectives	Endpoints
The secondary safety objective of the double-blind phase (see secondary double-blind objective)	The secondary safety endpoint of the double-blind phase (see secondary double-blind endpoint)
To evaluate molecularly confirmed a , symptomatic COVID-19 b	Incidence of symptomatic COVID-19 cases starting at 28 days after last vaccination
To evaluate molecularly confirmed a , severe/critical COVID-19 b	Incidence of severe/critical COVID-19 cases starting at 28 days after last vaccination
To evaluate molecularly confirmed a COVID-19 b requiring medical intervention (based on objective criteria)	Incidence of COVID-19 cases requiring medical intervention, starting at 28 days after last vaccination
To evaluate COVID-19 related death	Incidence of COVID-19 related deaths starting at 28 days after last vaccination

Objectives	Endpoints
To describe the severity of breakthrough infections	The severity of COVID-19 cases may be evaluated by the severity and number of symptoms (severity) of COVID-19 cases, ratio of severe/critical COVID-19 cases and ratio of long COVID-19 cases (duration of more than 28 days)

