To estimate potential correlate of risk/efficacy in relation to the primary endpoint of the main study and serious disease, hospitalization, and death based on immune responses in breakthrough cases compared to non-infected participants.	Levels of immune responses (antibody titers) and RNA sequencing analysis as available for participants having COVID-19 compared to non-infected participants.

a Molecularly confirmed COVID-19 is defined as a positive SARS-CoV-2 viral RNA result by a central laboratory using a RT-PCR based or other molecular diagnostic test.

b Per case definition for moderate to severe/critical COVID-19 as determined by the Clinical Severity Adjudication Committee (see below).

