To evaluate the primary and secondary endpoints utilized in the double-blind portion of the study in this unblinded booster portion of the trial in participants primed or boosted with Ad26.COV2.S, mRNA, inactivated, protein, and other adenovector-based vaccines during the time participants have and have not been boosted.	
 
Description of the primary and secondary endpoints (Day 28 after vaccination), such as symptomatic, severe/critical disease, hospitalization, and death, in the double-blind portion of the study as applicable as described in the first primary objective and first secondary objective including variants of concern and reference variants.
 

To estimate a correlate of immunity (correlate of risk) in relation to the primary endpoint of the main study and serious disease, hospitalization, and death based on immune responses at Day 28 after booster vaccination in boosted compared to non-boosted participants.	
 
Serological response to vaccination and antibody titers (VNA) against the original strain, 28 days after Ad26.COV2.S (<math>5 \times 10^{10}</math> vp dose level) single-dose booster vaccination.
 

To estimate potential correlate of risk/efficacy in relation to the primary endpoint of the main study and serious disease, hospitalization, and death based on immune responses in breakthrough cases compared to non-infected participants.	
 
Levels of immune responses (antibody titers) and RNA sequencing analysis as available.
 

Objectives	Endpoints
To compare the immune responses in the Heterologous and Homologous Booster Subsets 28 Days following booster dose administration.	
 
Qualitative comparison of responses in terms of binding, neutralizing antibody against Wuhan reference strain and variants of interest utilizing wtVNA and/or psVNA, depending on feasibility.
 
Analysis of antibodies binding to the SARS- CoV-2 S protein by ELISA.
 

To evaluate SARS-CoV-2 infection (severe/critical, moderate to severe/critical, symptomatic, and asymptomatic infections, that are serologically and/or molecularly confirmed**) for the different cohorts	
 
Incidence of SARS-CoV-2 infections (serologically and/or molecularly confirmed**).
 

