Visit Type	Screening	Vaccination	Safety and Immuno	Safety and Immuno	Safety and Immuno		Safety and Immuno	Immuno	Safety and Immuno	Safety and Immuno	Safety and Immuno	Safety and Immuno	Early Exit
Pulse oximetry		●											
Randomization		●											
Nasal sample collection for SARS CoV 2 testing n		●			● ll								
Biomarker RNAseq blood sample / transcriptomics (PAXgene tubes, whole blood), mL o		●2.5	●2.5						● t,ss 2.5				
Blood sample collection for screening serological test for anti SARS CoV 2 antibody	● p												
MRU questionnaire (baseline version) q		●											

Phase	Screening a	Study Period									Long-term Follow-up		
		1	2	3	4	5	6	7 ++	8 +	9 +	10	11	
Visit number b		1	2	3	4	5	6	7 ++	8 +	9 +	10	11	Exit c
Visit Timing		Vac	Vac + 28 d	Vac + 70 d	Vac + 24 w/ Post EUA, conditional licensure or approval in any country	Primary Vac +52 w	Booster +1 d	Booster +28 d	Booster +72 d	Booster +24 w	Booster +52 w		
Visit Day/Week	Day -28 to 1	Day 1	Day 29	Day 71	Month 6 (Week 24)/ Unblinding Visit	Year 1 (Week 52)/ Booster Visit	Year 1 +1 Day	Year 1 +28 Days (Week 56)	Year 1 +72 Days (Week 62)	Month 18 (24 weeks after Year 1 Visit)	Year 2 (52 weeks after Year 1 Visit)		
Visit Window			±3 d	±3 d	As soon as possible post Day 71 visit**	Preferably 6 months, but at least 3 months after last COVID-19 vaccination***	+1 d	±3 d	±3 d	±28 d	±28 d		
Visit Type	Screening	Vaccination	Safety and Immuno	Safety and Immuno	Safety and Immuno	Safety and Immuno	Immuno	Safety and Immuno	Safety and Immuno	Safety and Immuno	Safety and Immuno	Early Exit	
Pre vaccination symptoms r		●			●*	●							
eCOA training and set up s		●											
Distribution of thermometer		●											
Distribution of pulse oximeter t		●											
Distribution of MA COV form u		●											
Training and distribution: nasal swab kit and saliva recipients		●											

Phase	Screening a	Study Period									Long-term Follow-up		
		1	2	3	4	5	6	7 ++	8 +	9 +	10	11	
Visit number b													
Visit Timing		Vac	Vac + 28 d	Vac + 70 d	Vac + 24 w/ Post EUA, conditional licensure or approval in any country	Primary Vac +52 w	Booster +1 d	Booster +28 d	Booster +72 d	Booster +24 w	Booster +52 w		

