- z. All (S)AEs related to study procedures or non-investigational sponsor products will be reported from the time a signed and dated ICF is obtained until the end of the study/early withdrawal. All other SAEs are to be reported from the moment of vaccination until completion of the participant's last study-related procedure. AEs leading to study discontinuation (regardless of the causal relationship) are to be reported from the moment of vaccination until completion of the participant's last study-related procedure. Applicable from the time of local approval of protocol Amendment 5 onwards: Suspected AESIs are to be reported from the moment of vaccination until completion of the participant's last study-related procedure (see Section 8.3.1). Special reporting situations, whether serious or non-serious, are to be recorded from the time of each vaccination until 28 days post-vaccination (applicable for both the double-blind and open-label phases of the study). Participants will be reminded once a month to contact the study site in case of an SAE.
- aa. Refer to Section 6.10 for collection and recording of concomitant therapies associated with SAEs, solicited and unsolicited AEs, suspected AESIs, and MAAEs.
- bb. To be collected pre-vaccination only from participants receiving Ad26.COV2.S (after unblinding and/or as booster vaccination at Year 1/Booster Visit) and 28 days post booster vaccination (if applicable). Whole blood samples will be used for a complete blood count, including platelets, in a local laboratory or a substitute for local laboratory, depending on local feasibility towards turnaround time of sample processing. Serum samples will be derived from the whole blood sample and stored for potential future coagulation-related testing in a central laboratory if the participant experiences a suspected AESI (see Section 10.2, Appendix 2).
- cc. Blood sample for humoral immunity at Day 1 (pre-vaccination), Day 29, Day 71, Month 6/Unblinding Visit, Year 1/Booster Visit (pre-vaccination, if applicable), Year 1 + 28 days for participants who received booster vaccination, Year 1 + 72 days for participants who received booster vaccination, and Month 18 (24 weeks after Year 1 Visit), also includes sample for sero-confirmation of SARS-CoV-2 infection.
- dd. Blood samples for immunogenicity will only be taken if the early exit visit is at least 10 days after the previous immunogenicity blood draw.

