- ee. Blood sample for humoral immunity at Day 1 (pre-vaccination), Day 29, Day 71, Month 6/Unblinding Visit, Year 1/Booster Visit (prior to booster vaccination, if applicable), Month 18, and Year 2, and additionally 28 days and 72 days after booster vaccination, if applicable, also includes sample for sero-confirmation of SARS-CoV-2 infection. Samples will be collected for 400 participants at selected sites.
- ff. Enrollment into the Homologous Booster Subset and Heterologous Booster subset will start once operationally feasible. Blood sample for humoral immunity at the Year 1/Booster Visit (pre-vaccination) and 28 days, 72 days, 6 months, and 1 year after booster vaccination, also includes sample for sero-confirmation of SARS-CoV-2 infection. Samples will be collected for 600 participants at selected sites.
- gg. A subset of participants (N=6,000; Safety Subset) will record solicited signs and symptoms (including body temperature) in an e-Diary via the eCOA from the time of vaccination until 7 days after double-blind vaccination.

- hh. All other unsolicited AEs will be reported for the vaccination from the time of vaccination until 28 days after double-blind vaccination. In order to perform the safety assessment after 2,000 participants have been vaccinated in Stages 1a and 2a, participants will be asked to reach out to the study site as soon as possible in case they experience a serious or severe adverse event.
- ii. If within 28 days of the vaccination.
- jj. A ruler to measure local injection site reactions will be distributed to each participant in the Safety Subset.
- kk. To be repeated pre-vaccination if previous test was >1 day ago. Participants who originally received placebo and will not be receiving the Ad26.COV2.S vaccine under EUA, do not need to complete a pregnancy test.
- ll. To be repeated pre-vaccination if previous sample was >3 days ago.
- mm. To be repeated pre-vaccination if previous sample was >5 days ago.
- nn. The approximate blood volume collected depends on whether the participant is in one of the immunogenicity subgroups and/or received Ad26.COV2.S booster vaccination at the Year 1/Booster Visit.
- oo. Those participants in the Immunogenicity Subset that transfer to the Homologous Booster Subset at the Year 1/Booster Visit will from that visit onwards follow the humoral immunogenicity sample schedule of the Homologous Booster Subset and discontinue the schedule of the Immunogenicity Subset.

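### The booster gene-expression endpoint is to be compared with post-cross-over responses in this study, but the schedule collects no sample from which those responses could be measured

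*Protocol*

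**What the plan says.** **Gene expression.** Section 3.2.2 (Exploratory, Booster Phase) specifies "mRNA sequencing immediately after immunization up to 28 days after vaccination analyzed in participants who received booster vaccination". The comparator is "compared to responses after primary immunization following immunization of cross-over participants from the placebo group at unblinding in VAC31518COV3001", with VAC31518COV2008 named beside it. Section 3.3 repeats the endpoint for the passive follow-up phase. The parent objective concerns a subset of the booster subsets, sampled pre-boost and 1 and 28 days after, subject to feasibility.

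**What is collected.** In Section 1.3.3 the row "Biomarker RNAseq blood sample / transcriptomics (PAXgene tubes, whole blood), mL" has entries at Day 1, Day 29 and Year 1 + 28 days, the last for boosted participants only. About 60 + 60 booster-subset participants also give RNA pre-boost, at +1 day and at +28 days. Serum for non-subset participants follows footnote cc: "Blood sample for humoral immunity at Day 1 (pre-vaccination), Day 29, Day 71, Month 6/Unblinding Visit, Year 1/Booster Visit (pre-vaccination, if applicable", and later visits. Footnote mm says of the Month 6 serum "To be repeated pre-vaccination if previous sample was >5 days ago", so it is drawn before the cross-over dose. Footnote bb makes the 7 mL clinical laboratory sample pre-vaccination too.

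**Booster correlate.** A secondary objective (Synopsis 2.2 and Section 3.2.2) estimates a correlate of risk "based on immune responses at Day 28 after booster vaccination in boosted compared to non-boosted participants". Its endpoint lists only titers 28 days after the booster.

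**The concern.** An endpoint that names a comparator for which no sample is collected cannot be computed. The analyst must then substitute another comparator after the data are in, and the choice may shape the result. Here the natural comparison is the early transcriptional response to a first Ad26.COV2.S dose against the response to a booster. The group named for the first-dose response is the one group that has no RNA sample in the relevant window. For placebo recipients, the Day 1 and Day 29 PAXgene samples precede any active vaccine.

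The correlate objective has a milder form of the same problem. Non-boosted participants have no booster date from which to count 28 days and no draw at that visit. Boosted versus non-boosted is also a contrast of vaccination status, whereas a correlate of risk relates a marker to case status.

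**Working it through.** **Step 1. Reproduce the stated blood volumes (Section 1.3.3).** Components: serum 10 mL (non-subset) or 15 mL (subset), clinical laboratory 7 mL, PAXgene 2.5 mL, cytokine 5 mL.

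| Visit | Minimum | Maximum | Stated per visit | Cumulative (matches stated) |
|---|---|---|---|---|
| Day 1 | 10 + 2.5 | 15 + 2.5 | 12.5-17.5 | 12.5-17.5 |
| Day 29 | 10 + 2.5 | 15 + 2.5 | 12.5-17.5 | 25.0-35.0 |
| Day 71 | 10 | 15 | 10.0-15.0 | 35.0-50.0 |
| Month 6 | 10 + 7 | 15 + 7 | 17.0-22.0 | 52.0-72.0 |
| Year 1 | 10 | 15 + 7 + 5 + 2.5 | 10.0-29.5 | 62.0-101.5 |
| +1 day | 0 | 5 + 2.5 | 0.0-7.5 | 62.0-109.0 |
| +28 days | 0 | 15 + 7 + 5 + 2.5 | 0.0-29.5 | 62.0-138.5 |
| +72 days | 0 | 15 | 0.0-15.0 | 62.0-153.5 |
| Month 18 | 10 | 15 | 10.0-15.0 | 72.0-168.5 |
| Year 2 | 0 | 15 | 0.0-15.0 | 72.0-183.5 |

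All ten per-visit and all ten cumulative ranges reproduce exactly, so the table can be relied on despite broken columns in the extracted text.

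**Step 2. Is there a PAXgene tube at Month 6?** With one, the range would be 17.0 + 2.5 = 19.5 to 22.0 + 2.5 = 24.5 mL. The stated range is 17.0-22.0 mL, so there is none. Blood drawn at that visit would in any case precede the dose.

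**Step 3. When is the next scheduled visit?**
- Nominal gap: (52 − 24) × 7 = 196 days.
- Preferred windows, reading the lower limits as −106 and −100 days (an assumption; the minus signs appear lost in extraction): shortest gap (364 − 100) − (168 + 28) = 68 days; longest gap (364 + 170) − (168 − 106) = 472 days.
- Where a booster is given, the 3-month minimum after the last vaccination raises the lower end to about 90 days.

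Even the shortest gap exceeds 28 days. The first scheduled RNA sample after a cross-over dose is the pre-boost tube at Year 1. It is taken only from those cross-over participants who fall among the roughly 60 sampled in the Homologous Booster Subset.

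**Step 4. Which scheduled samples show a first-dose response?** Day 29 is 28 days after the Day 1 vaccination, and every participant has a PAXgene tube at Day 1 and Day 29. In the double-blind Ad26.COV2.S group these samples give a change over 28 days that is time-matched to pre-boost and booster + 28 days. No +1 day sample follows primary vaccination.

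**Step 5. Non-boosted participants at Day 28.** The + footnote limits Visits 8 and 9 to participants boosted inside or outside the study. The 0.0 mL minimum at +28 and +72 days agrees.

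**The case against.** **Feasibility and a second comparator.** The gene-expression objective is exploratory, depends on feasibility, covers about 120 people and also names VAC31518COV2008. This lowers the stakes. It does not supply the within-study sample, since the feasibility clause concerns sampling around the booster. What VAC31518COV2008 collected cannot be checked here.

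**Unseen text.** Only Part 1 is available. Sections 8.1.4, 8.5, 8.9 and 9.8.2 could add or explain sampling. That limits confidence, although the schedule of activities is visible in full and shows none.

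**Blood outside the schedule.** Until Amendment 7, suspected COVID-19 episodes, including swab-negative ones, can yield serum and RNA between cross-over and Year 1. Such samples come from symptomatic people at arbitrary times and are not the planned post-dose comparator.

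**Non-boosted participants are sampled.** A reader might infer that they never are. That is wrong: they give serum at Year 1 and, before Amendment 7, at Month 18, and the Immunogenicity Subset continues to Year 2. Only a matched Day 28 value is missing. The objective also refers to the primary endpoint, so some case contrast may be intended.

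**A stronger reading of the cross-over correlate.** That objective is framed "based on immune responses in breakthrough cases compared to non-infected participants". Because the late vaccinated cohort has no scheduled post-dose serum until Year 1, one might infer that illness samples will be used and that reverse causation follows. The documents do not support this. No passage says post-infection samples will be the marker. The double-blind per-protocol immunogenicity definition excludes them and is the stated basis for correlates of risk. The endpoint is limited to what is available, and early-cohort Day 29, Day 71 and Month 6 sera can inform it. Sample selection for the open-label phase is left to the SAP.

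**Conclusion.** The point holds for the gene-expression endpoint. Zero PAXgene samples are scheduled between the cross-over dose and Year 1, against an endpoint that spans the first 28 days. The named within-study comparison therefore cannot be computed. This rests on the schedule in Section 1.3.3, confirmed by the blood volumes, and on Part 2 adding no sampling that the schedule omits.

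It does not follow that the study has no usable first-dose comparator. The double-blind active group has Day 1 and Day 29 tubes, and the endpoint simply names the wrong group.

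The correlate objective has a smaller defect: the contrast as worded has no matching non-boosted draw and is not itself a case versus non-case contrast. Confidence is lower here because Section 9.8.2 is unseen.

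Both are reconciliation matters in exploratory and secondary open-label objectives. The co-primary efficacy analysis is unaffected.

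**What to change.** 1. In Sections 3.2.2 and 3.3, replace the cross-over comparator with the Day 1 and Day 29 PAXgene samples of the double-blind Ad26.COV2.S group, compared with the pre-boost and Day 28 post-boost samples.
2. Compare the +1 day post-boost sample only with the participant's own pre-boost sample or, if that study sampled at the same time, with VAC31518COV2008.
3. In Synopsis 2.2 and Section 3.2.2, restate the booster correlate as cases versus non-cases among boosted participants whose Day 28 post-boost sample was taken before infection. Show non-boosted Year 1 values descriptively.

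The cost is wording only; every sample used is already scheduled. The new comparator has one limit. Boosted participants first randomized to Ad26.COV2.S can serve as their own controls, but those first randomized to placebo, including the whole Heterologous Booster Subset, can be compared only between persons. The text should say so.
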